### 4.3. Target population

Inclusion criteria: Asymptomatic men and women between 50 and 69 years of age. This cutoff of age is the recommended by the Spanish Screening Network for the implementation phase of the Spanish CRC screening program. Thereafter, it is planned to increase this age cutoff to 74 years when the screening program will be extended to the whole country (unfortunately, this stage has not been accomplished at the end of COLONPREV study).

Permanent exclusion criteria: All individuals who meet any of the following conditions will be permanently excluded:

- Personal history of inflammatory bowel disease, colorectal polyps, colorectal adenoma or CRC.
- Family history of familial adenomatous polyposis syndromes or other hereditary polyposis syndromes, hereditary nonpolyposis colorectal cancer (diagnosed by the presence of germline mutation in DNA repair genes and/or meeting the Amsterdam II criteria), 2 or more first-degree relatives with CRC or 1 first-degree relative with CRC diagnosed before the age of 60.
- Severe comorbidity that involves a poor short-term prognosis (disease with a mean life expectancy of less than 5 years) or chronic disease that involves major limitation of physical activity (performance status  $\geq 2$ ).
- Individuals who have had a total colectomy.

Temporary exclusion criteria: All individuals who meet any of the following conditions will be temporarily excluded:

- Those who have undergone any of the examinations used in CRC screening, regardless of the reason, within the periods specified: history of FOBT screening in the past 2 years, or sigmoidoscopy or colonoscopy within the past 5 years (as long as its validity is documented) (to avoid this eventuality we will seek to conduct the study in a healthcare setting in which the population has not been screened previously). Such individuals may enter the study after the time periods mentioned have expired.

- Those showing symptoms suggestive of colorectal disease (rectal bleeding, altered frequency of bowel movements, constitutional symptoms, anaemia). These individuals may enter the study once their condition has been studied and a colorectal cancer or other pathology that would constitute a cause of permanent disqualification has been excluded, and if any of the above-mentioned tests were performed, once the periods mentioned in the previous section have expired.

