- Participants in either Group 1 or Group 2 in whom only 1 or 2 non-advanced adenomas (low-risk adenomas) are detected, will be included in a surveillance programme and offered a new colonoscopy at 5 years.
- Participants in either Group 1 or Group 2 in whom 3 or more non-advanced adenomas or 1 or more advanced adenomas (high-risk adenomas) are detected will be included in a surveillance programme and offered a new colonoscopy after 3 years.
- Participants in either Group 1 or Group 2 in whom >10 adenomas are detected in a single examination will be scheduled for surveillance colonoscopy in less than 3 years.
- Participants in either Group 1 or Group 2 in whom a large sessile adenoma is detected and removed by piecemeal resection will undergo a colonoscopy in 2-6 months to verify complete removal.

- The interval between subsequent surveillance colonoscopies will depend on the findings of the earlier examinations. In general, if a neoplastic lesion is detected, the above-mentioned criteria will be applied. On the other hand, if the examination is normal or if only non-neoplastic disease is detected, the next colonoscopy will be performed 5 years later.
- For participants in either Group 1 or Group 2 in whom a malignant polyp is detected (pT1N0M0) and for whom endoscopic polypectomy is deemed sufficient (see criteria below), a new colonoscopy will be performed with biopsy of the resected area within a period of no more than 2-3 months to confirm that complete resection of the lesion was achieved. Subsequently, new colonoscopies will be performed after 1 and 3 years.
- Participants in either Group 1 or Group 2 in whom an invasive CRC is detected will be treated and followed up according to the specific protocol of each centre, but always including a colonoscopy 1 year after the resection, and every 3 years thereafter.

Any individual may refuse the screening examination assigned and request an alternative method. Any such individual will be assessed according to the group to which he/she was randomised for the “intention to screen” analysis, and according to the procedure actually performed in the “as-screened” analysis. These same criteria will be applied when any screening examination is performed (FOBT, colonoscopy, CT-colonography, or colonic capsule) and that is not foreseen in the study, regardless of the reason.

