## 6.3. Classification of colorectal cancer

CRC patients detected in the study will be classified as: 1) *Screening CRC*: CRC detected in the screening Groups 1 and 2; 2) *Interval CRC*: CRC diagnosed after a negative FIT (Group 1) or after a negative colonoscopy (Group 2), or detected after a positive FIT with a negative colonoscopy or if colonoscopy was not accepted by the patient (Group 1); 3) *Sporadic CRC*: CRC diagnosed in patients that did not accept screening in the study.

CRC stage will be established using TNM classification (*American Joint Committee on Cancer*, 6th edition):

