## 7. STATISTICAL ANALYSIS PLAN (SAP)

Because of the study design, which allows for cross-over between both strategies, the main outcomes of the study will be analysed by intention-to-screen, as-screened and per-protocol.

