### As-screened

Cumulative incidence curves for the screening procedure actually performed will be estimated with the Kaplan-Meier estimator, considering the period from the day of randomization to the end of follow-up. The Kaplan-Meier estimator with daily outcome events will be used to compute the probability (risk) of the outcome during the period. For CRC incidence and mortality, non-CRC events will be considered as censoring events. We will calculate the 10-year risk differences and risk ratios between the trial arms, and 95% CI will be computed using the normal approximation. To provide adjusted estimates, the Kaplan-Meier estimator will be weighted with inverse probability of weighting (IPW). In this causal contrast, propensity scores for colonoscopy, FIT and no screening will be estimated with a multinomial logistic regression. The included covariates will be age, sex and centre of participants with a 3-degree of freedom natural spline.

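### The as-screened rule lets a colonoscopy done to diagnose a symptomatic cancer decide who counts as screened by colonoscopy, which can reverse the as-screened comparison but leaves the intention-to-screen test untouched

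*Combined protocol and SAP*

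**What the plan says.** Section 7 gives the as-screened analysis a formal place: "the main outcomes of the study will be analysed by intention-to-screen, as-screened and per-protocol". Section 5 sets the grouping rule. A person who refuses the assigned test and asks for another is analysed by randomised group for intention to screen, and by the procedure received for the as-screened analysis. The next sentence extends these criteria to the case "when any screening examination is performed (FOBT, colonoscopy, CT-colonography, or colonic capsule) and that is not foreseen in the study, regardless of the reason".

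The As-screened part of section 7 adds three things:

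- Grouping: "Cumulative incidence curves for the screening procedure actually performed will be estimated with the Kaplan-Meier estimator".
- Time zero: "considering the period from the day of randomization to the end of follow-up".
- Weighting: "The included covariates will be age, sex and centre of participants", used in a multinomial model for colonoscopy, FIT and no screening.

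Two other places bear on the reading. Section 4.3 temporarily excludes "Those who have undergone any of the examinations used in CRC screening, regardless of the reason, within the periods specified". Section 6.3 defines sporadic CRC as "CRC diagnosed in patients that did not accept screening in the study", but does not say in which as-screened group such a person is analysed.

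**The concern.** Colonoscopy is both a screening test and an ordinary route to diagnosing CRC in someone with symptoms. Suppose a non-participant bleeds, has a colonoscopy and is found to have cancer. If that examination sets the as-screened group, the person leaves no screening and enters colonoscopy because of the disease that the analysis counts. Exposure is then defined by the outcome.

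The planned method has no protection against this. Follow-up runs from randomisation, so an examination years later reclassifies the whole follow-up. Age, sex and centre say nothing about why the examination was done. No exposure window is given, and the examination is not required to precede the cancer diagnosis.

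At stake is the credibility of one of the three planned analyses of the main outcomes. Two analysts applying the rule in good faith could code the same person differently and reach opposite as-screened conclusions about FIT and colonoscopy.

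**Working it through.** The documents give no expected figure for the as-screened analysis, so there is none to reproduce. The check asks how much relabelling would reverse it.

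**Inputs from section 4.5:** 27,749 per arm (55,498 in total); 30% expected overall compliance; modelled mortality reductions of 51% (FIT) and 75% (colonoscopy).

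**Assumptions:**
- The 30% applies to each arm, everyone screened takes the assigned test, and FIT participants are not moved.
- The modelled reductions apply to participants.
- *r* is the 10-year CRC death risk in the unscreened.
- *g* is the share of unscreened people who have a non-study colonoscopy and so move to the colonoscopy group.
- *x* is the share of unscreened CRC deaths that move with them.

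The documents give no value for *r*, *g* or *x*.

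**Group sizes:** colonoscopy 0.30 × 27,749 ≈ 8,325; FIT the same; unscreened 0.70 × 55,498 ≈ 38,849. Let k = 8,325/38,849 = 0.2143.

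**Correct classification:** the colonoscopy/FIT mortality ratio is 0.25/0.49 = 0.51. At an assumed *r* of 0.5%, expected deaths are about 10.4 (colonoscopy), 20.4 (FIT) and 194 (unscreened).

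**Apparent risks after relabelling, divided by *r*** (which cancels from every ratio):
- Colonoscopy: (0.25k + x)/(k + g)
- FIT: 0.49
- No screening: (1 − x)/(1 − g)

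**Colonoscopy looks worse than FIT** when x > 0.24k + 0.49g = 0.0514 + 0.49g.

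**Colonoscopy looks worse than no screening** when x > [k + g − 0.25k(1 − g)]/(1 + k). At g = 0 this is (0.2143 − 0.0536)/1.2143 = 0.132.

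**Neutral point:** the colonoscopy/FIT ratio stays at 0.51 when (0.25k + x)/(k + g) = 0.25, that is, when x = 0.25g. Below that, the bias favours colonoscopy.

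| g | neutral x | x above which colonoscopy looks worse than FIT | x above which it looks worse than no screening |
|---|---|---|---|
| 0 | 0 | 5.1% | 13% |
| 10% | 2.5% | 10.0% | 22% |
| 20% | 5.0% | 14.9% | 31% |
| 30% | 7.5% | 19.8% | 39% |

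At g = 0 and *r* = 0.5%, the first threshold is about 10 of 194 deaths. In the other direction, g = 30% with x = 5% gives (0.0536 + 0.05)/(0.2143 + 0.30) = 0.201, and 0.201/0.49 = 0.41, which flatters colonoscopy.

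**Sensitivity to uptake:** over g from 0 to 30%, the threshold against FIT runs from 3% to 18% at 20% uptake (k = 0.125) and from 12% to 27% at 50% uptake (k = 0.5).

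**The case against.** The strongest reply is textual. Section 5 speaks of a screening examination and section 7 of a screening procedure, and a colonoscopy prompted by bleeding is not naturally either. The preceding sentence concerns people who decline the assigned test and ask for another, so the closing phrase may mean only whatever the reason for departing from the assignment. Section 4.3 uses broader words, "Those who have undergone any of the examinations used in CRC screening, regardless of the reason", for a different purpose, namely eligibility. Section 6.3 shows that the plan does distinguish cancers in non-acceptors.

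Much of this stands. A reader might infer that the plan plainly orders every colonoscopy to reclassify people. The documents do not go that far, because a screening-only reading is possible. It is not secured, though. The parenthesis in section 5 lists test types without indications, the closing phrase is unqualified, the same phrase in section 4.3 covers any indication, and section 6.3 labels cases without assigning them to an analysis group.

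A second reply is that only counting relabelled cancers exaggerates the effect, because the literal reading also moves people examined and found free of cancer. This is right and it matters. With g = 20%, moving 25% of unscreened deaths gives a colonoscopy/no-screening ratio of about 0.78 (0.733/0.9375), against about 1.9 (1.417/0.75) at g = 0. Moving 50% gives about 2.1 (1.336/0.625). Reversal remains possible but needs a larger share.

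A third is that the 51% and 75% are modelled for a hypothetical population aged 50, and that section 4.5 introduces the modelling with colonoscopy every 10 years, not once. Applying them to participants here is an assumption.

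**Conclusion.** The concern holds as an ambiguity that permits outcome-dependent classification and, on the more literal reading, requires it. Under the stated assumptions at 30% uptake, relabelling roughly 5% to 20% of unscreened CRC deaths makes colonoscopy look worse than FIT, and roughly 13% to 39% makes it look worse than no screening, as *g* goes from 0 to 30%. The thresholds do not depend on the mortality level. They do depend on uptake, on the modelled reductions and on *g*. Whether the actual relabelled share would exceed them cannot be settled from the documents.

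A reader might infer that the trial's non-inferiority result could be reversed, or that the rule always works in favour of FIT. Neither is supported. Section 4.5 ties the 1.6% margin to intention to screen, where people stay in their randomised arm, and no document attaches that margin to the as-screened analysis. The direction also varies: if many cancer-free people move with few deaths, the bias favours colonoscopy. In either direction the as-screened estimate would partly reflect the coding rule and not the screening.

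**What to change.** In section 5 and in the As-screened part of section 7, replace the open-ended closing phrase, for the as-screened analysis, with a rule along these lines:

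- Only an examination done as screening in a person without symptoms (the assigned test or a requested alternative), within a stated exposure window and before any CRC diagnosis, sets the as-screened group.
- Examinations prompted by symptoms or clinical suspicion leave the group unchanged.
- Colonoscopy after a positive FIT stays with FIT.
- Sporadic CRC, as defined in section 6.3, in a person with no screening examination counts in the no-screening group.
- Results are shown with and without examinations whose indication is unknown.

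The window and the indication rule are both needed. A window removes late diagnostic examinations but not those that fall inside it.

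The cost is a few sentences, plus coding the indication of non-study examinations from records. Indication will be missing for some outside examinations, which is why the last item is there. The intention-to-screen analysis needs no change.

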## 5.1. Screening phases

### Phase 1:

- It begins when the presentation letter, containing information on the CRC screening programme and the rationale of the study, is sent.
- Four weeks later, the invitation letter indicating in which screening strategy the individual has been allocated, is sent.
- It ends with receipt of the FIT test results (and performance of colonoscopy in those individuals with a positive result) (Group 1), or after completion of colonoscopy (Group 2).

### Phase 2 (individuals who require retesting):

- In Group 1, it begins with repetition of the FIT test in patients for whom the previous test was invalid and ends when it is delivered and properly read.
- In Group 2, it begins with repetition of colonoscopy in cases in which the bowel preparation was inadequate, or repetition of colonoscopy or performance of CT-colonography when the colonoscopy was incomplete.

Phase 3: includes all Group 1 respondents for phases I and II who are included in the subsequent biennial rounds until completion of the 10 years. In Group 2, phase III will be completed 10 years after completion of the first examination.

## **5.2. Organisation and management of the project**

To ensure the viability and effectiveness of this project the following is necessary: 1) Ensuring specific CRC prevention units (CRCPU) in the gastroenterology departments of each participating hospitals; 2) Effective coordination between hospital CRCPU, LSO and primary care physicians; 3) Implementation of an educational programme for the general population and primary care physicians; 4) Assurance of the development of the above-mentioned field work and an effective system for recording the results of the programme in order to determine its true impact and to correct potential malfunctions; and 5) The provision of the financial resources required for ensuring the viability of the project.

### CRC prevention units (CRCPU)

These units will be located in the Gastroenterology Departments of each participant hospitals. They will have a coordinator and will work with a separate agenda in order not to interfere with the regular activity of the endoscopy units. People with a positive FIT as well as all participants in the Group 2 that accepted colonoscopy will be received in these CRCPU. These units should warrant a correct diagnosis, treatment and surveillance of participants. Finally, CRCPU will give assistance to individuals identified as having a high risk for developing CRC.

### Coordination between Local Screening Offices and primary care physicians

The LSO will have a person responsible for the study. There will be also a study coordinator in each Health Care Centre participating in the study, who will be responsible for its development. Moreover, it will be a data collector in charge of the information task and recruitment; this data collector could be located at the LSO, Health Centre or CRCPU.

### Educational programme and measures for improving study participation

The educational programme is aimed to improve the knowledge of the target population and primary care physicians on natural history of CRC, symptoms, treatment, prognosis, and diagnostic tests in order to improve participation in the study. This aspect is critical to achieve a high adherence with screening.

Possible actions include informative leaflets about CRC screening, campaign in the media (TV, radio and press), programme web page, organization of a "CRC prevention awareness day", among others (see Quality assurance programme).

### Data recording

Demographic data, results of diagnostic tests, treatments and pathological data will be recovered in an online, centralized and protected database ([www.coloncrib.org](http://www.coloncrib.org)).

## 6. DEFINITIONS

- *Pragmatic study*: study designed to clarify whether an intervention works under real-life conditions and whether it works in terms that matter to the patient. It is simply concerned with whether the intervention works, not how or why.
- *Target population*: 50-69 year-old individuals with verified address in sanitary card.
- *Invited population*: target population excluding non-contacted individuals.
- *Eligible population*: target population excluding non-contacted and excluded individuals.
- *Participant population*: individuals who returned the FIT test (Group 1) or who completed colonoscopy (Group 2).
- *Screening inclusion data*: data of sending the invitation letter.
- *Incomplete colonoscopy*: colonoscopy in which caecal intubation is not possible. When an incomplete colonoscopy occurs, this examination must be repeated or completed with a CT-colonography.
- *Inadequate colon cleansing*: when less than 90% of colorectal mucosa can be properly evaluated due to the presence of faeces, this examination must be repeated.
- *Non-neoplastic polyp*: hyperplastic, hamartomatous or inflammatory polyps.
- *Non-advanced adenoma*: any tubular adenoma <1 cm and with low-grade dysplasia.
- *Advanced adenoma*: adenoma >1 cm in size, or with high-grade dysplasia, or with villous component (>25%).
- *High-risk adenoma*: 3 or more non-advanced adenomas, or any advanced adenoma.
- *Low-risk adenoma*: 1 or 2 non-advanced adenomas.
- *Non-invasive colorectal cancer*: colorectal carcinoma without submucose invasion (pTis). It includes intramucous carcinoma and intraepithelial carcinoma.
- *Invasive colorectal cancer*: colorectal carcinoma beyond the *muscularis mucosa* (pTNM stages I, II, III and IV).
- *Advanced neoplasia*: colorectal advanced adenoma or cancer.
- *Malignant polyp*: adenoma that harbours an area of carcinoma invading submucose (pT1).
- *Polyposis*: existence of >10 polyps. Depending on the histology, it could be adenomatous, hamartomatous or hyperplastic.
- *Non-neoplastic colorectal diseases*: any non-neoplastic disease detected in the colonoscopy (i.e. haemorrhoids, diverticulosis, angiodyplasia, etc.).

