#### **4.6. Processes of selecting and inviting the population to be screened**

In each Autonomous Region, randomisation will be done prior to sending the invitation letter (Zelen's design) in order to properly assess the participation in each screening group and perform the intention to screen analysis of the results.

The selection process will be the same as the one used in the Nottingham study (14), in which compliance with the programme reached 60%. Briefly, target population will be identified from the Community Health Registry (CHR) of each Autonomous Region. The CHR is based on the population registry, and includes unique identification for each person, such as name, date of birth, social security number, and contact address, and it is updated regularly to account for population migration, deaths and changes in personal details. This list will be refined using cancer registries or other sources of information (primary care medical records, hospital databases, etc.) in order to eliminate individuals who meet exclusion criteria (i.e. CRC and colorectal adenoma) or who have died. Prior to randomisation, individuals will be clustered by household. With such an approach, it is hoped to ensure that all individuals in one household will be assigned to the same study group.

All individuals will receive an initial, pre-invitation letter by mail (which may be signed by their primary care doctor or an area specialist, or the person responsible for the Autonomous Regions screening programme) with information regarding the relevance of CRC as a health problem, the possibility of preventing it by means of screening, and the impending start up of a pilot programme (**presentation letter**), along with an informative leaflet which explains existing measures for CRC prevention. They will later be sent a second letter (also signed by their primary care doctor or area specialist, or the person responsible for the Autonomous Regions screening programme) in which they are invited to participate in the study (**invitation letter**) and includes an appointment to the Local Screening Office (LSO) and a contact telephone number. In the invitation letter, individuals will also be informed of the screening option that applies to them, the characteristics of the test and its possible adverse effects. This whole process will be performed by the LSO (who may be assisted by staff of the project data manager).

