Individuals who do not respond will receive a **reminding letter** at 3-4 months after sending of the introduction letter. Individuals who do not respond to it will receive a second reminding letter 2 months later.

The content of the two letters will be identical in all Autonomous Regions. However, translation into official languages and the use of logos, institutional images or letterheads of each Autonomous Regions is permitted.

The frequency of sending invitation letters will be adapted to the capacity of each LSO to attend individuals wishing to participate in order to diminish the lag time between randomisation and participation to less than 3 weeks.

At the Health Centre, the functions of staff responsible for the study (including physicians and nurses of the centre and the data-collector in charge of the study) will be: 1) To track selected individuals in the sample who do not respond or who do not come to the appointment; 2) For those who come to the appointment, to confirm their suitability to participate in the study (compliance with inclusion/exclusion criteria); 3) To provide more detailed and exhaustive information about the study objective and the strategy they have been assigned in order to facilitate their participation; 4) To identify high-risk individuals, and assign them an appointment for a high-risk clinic of the reference hospital or the corresponding genetic counselling unit (see below); 5) To obtain written informed consent for participation in the study; 6) To complete the questionnaire with the data of all individuals contacted and include them in the project database; and 7) To provide a FIT kit (Group 1) or formalise the appointment at the hospital CRC prevention unit assigned to perform the colonoscopy (Group 2). In the event that an attending individual refuses to participate in the study, the baseline questionnaire will be completed and the reasons for the refusal of the invitation will be recorded. They will also be informed that even if they are not examined during screening, they will be contacted periodically in order to monitor the state of their health.

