#### Secondary end points:

1. *Participation, detection rate, diagnostic yield and complication rate at the completion of the first round and at the end of study (10 years)*

Definitions of these four key outcomes are as follows:

- Participation: number of participating individuals (i.e. individuals who completed colonoscopy in the colonoscopy group and individuals who returned the test in the FIT arm) relative to the number of eligible individuals.
- Detection rate: number of true positives relative to the number of participating individuals.
- Diagnostic yield: number of true positives relative to the number of eligible individuals.
- Complication rate: number of major complications (i.e. perforation, postpolypectomy bleeding requiring hospitalization, and cardiovascular/pulmonary complications requiring medical management) relative to the number of participating individuals.

Differences in these four key outcomes between both strategies will be established by logistic regression analysis, adjusted by age, gender and participating centre, and reported as odds ratios (OR) with 95% CI.

*2. Overall survival at the end of study (10 years)*

*3. CRC incidence at the end of study (10 years and 15 years)*

*4. Cost-effectiveness analysis*

Cost-effectiveness will be studied with a Markov's model at the completion of study. Results will be reported in terms of quality-adjusted life years (QALY).

*5. Analysis of factors influencing participation in the study*

Factors associated with participation at the completion of first round and at the end of study (10 years) in each screening strategies will be analysed by logistic regression analysis and results reported as OR with 95% CI. Parameters analysed will include demographics, personal and familial characteristics, socio-economic status, etc.

*6. Number needed to screen to detect a colorectal cancer*

The number needed to screen to detect a CRC will be calculated using the inverse of risk (i.e. the number of participants receiving a given screening modality divided by the number of positive cases in that given modality), with 95% CI computed using the inverse of the binomial standard approximation.

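### Diagnostic yield is compared per eligible person, but eligibility is settled after randomisation and mainly among attenders, so yield is slightly inflated in the arm with higher attendance

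*Combined protocol and SAP*

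**What the plan says.** Section 6 (Definitions) sets the eligible population as the "target population excluding non-contacted and excluded individuals". It gives no time point or source for the exclusions. In section 7 (SAP), item 1 of the secondary end points defines diagnostic yield as the "number of true positives relative to the number of eligible individuals". The arms are compared by logistic regression, "adjusted by age, gender and participating centre, and reported as odds ratios (OR) with 95% CI". No analysis of yield on all randomised people is specified.

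The order of events is in sections 4.4 and 4.6. Households are randomised from the health-card list before any letter is sent, and the invitation letter tells each person which test they have been allocated. Before randomisation the list is cleaned using cancer registries, primary care records and hospital databases; colorectal cancer, adenoma and death are the reasons named. The remaining criteria are checked by health centre staff, whose duties include: "For those who come to the appointment, to confirm their suitability to participate in the study (compliance with inclusion/exclusion criteria". Section 4.4 also says that all eligible patients are randomised, which does not fit well with eligibility being confirmed at a later visit.

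**The concern.** A denominator fixed after randomisation is safe only if people leave it by the same process in both arms. Here the process depends on attendance. Someone with a disqualifying family history, symptom, recent examination or comorbidity that the records missed leaves the denominator on coming to the appointment and being asked. The same person stays in the denominator if they do not come. Attendance is decided after the person has been told the allocated test, and the plan itself treats participation as something that may differ between arms. The arm with higher attendance therefore sheds more ineligible people, while its count of true positives is unchanged.

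At stake is the comparison of diagnostic yield, at the first round and at 10 years, and the reported percentages. Section 4.6 gives the intention-to-screen analysis as one reason for randomising before invitation. A denominator that depends on attendance gives up part of that benefit for this end point.

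**Working it through.** The plan gives no figure for this effect, so there is none to reproduce. What follows is an illustration.

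**Inputs from the documents.** N = 27,749 per arm and an expected overall compliance of 30% (section 4.5); 60% compliance in the earlier trial whose selection process is followed (section 4.6).

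**Assumed inputs.** A share e of people meet an exclusion criterion that the record search missed, and they are found only if they attend. Attendance is a, independent of e, so e is also the share of attenders excluded. I take e = 5%, 10% and 20%. The attendance pairs are 35/25% and 40/20%, both averaging the stated 30%, and 60/30% as an outer case.

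**Denominator.** Each arm keeps N(1 - e·a). With the same true-positive count in both arms, the yield ratio (higher- against lower-attendance arm) is multiplied by

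(1 - e·a_low) / (1 - e·a_high).

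| Attendance | e = 5% | e = 10% | e = 20% |
|---|---|---|---|
| 35/25% | 0.9875/0.9825 = 1.005 | 0.975/0.965 = 1.010 | 0.95/0.93 = 1.022 |
| 40/20% | 0.99/0.98 = 1.010 | 0.98/0.96 = 1.021 | 0.96/0.92 = 1.043 |
| 60/30% | 0.985/0.97 = 1.015 | 0.97/0.94 = 1.032 | 0.94/0.88 = 1.068 |

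With equal attendance the factor is 1 for every e.

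**One case in counts.** At e = 10% and 40/20% attendance, 1,110 and 555 people are removed, leaving denominators of 26,639 and 27,194. If true yield is 2% of the truly eligible in both arms (assumed), each arm has 27,749 × 0.9 × 0.02 ≈ 499 true positives. The observed yields are 1.88% and 1.84%, an odds ratio of 1.021 where the truth is 1. On all randomised people, both yields are 1.80% and the odds ratio is 1.

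**Effect on the test.** Assume a true yield of 1% or 2%, equal in both arms. Over e = 5-20%, the two-sided type I error of a nominal 5% test is 5.0-6.2% at 35/25% attendance and 5.2-9.8% at 40/20%. It reaches 16.8% only at the outermost combination (60/30%, e = 20%, yield 2%).

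**Participation odds ratio.** If every eligible attender completes the test, participation odds in an arm are (1 - e)a / [1 - e·a - (1 - e)a] = (1 - e)a / (1 - a). The factor (1 - e) cancels between arms. At 40/20% the odds ratio is (0.4/0.6)/(0.2/0.8) = 2.67 for any e. If only 80% of eligible attenders complete it and e = 20%, the odds ratio is 2.51 against a true 2.47. On all randomised people with full completion and e = 20%, it would be (0.32/0.68)/(0.16/0.84) = 2.47 rather than 2.67.

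**The case against.** The strongest case against the point is that the effect is small and partly guarded against. The list is cleaned from several sources before randomisation. Section 4.6 also has staff track people who do not respond or attend, and complete a questionnaire for everyone contacted. If exclusions are recorded by that route too, the imbalance shrinks. Symptoms and recent examinations are only temporary exclusions (section 4.3), so some of these people may enter later. With about 277 to 555 true positives per arm (1-2% of 27,749), the 95% half-width on the log odds ratio is 1.96 × √(2/277) = 0.17 to 1.96 × √(2/555) = 0.12, well above a bias of 0.5-4%. All of this stands and limits the size. It does not remove the mechanism, because no rule requires exclusions to be ascertained alike in attenders and non-attenders.

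Three stronger readings are tempting, and the documents do not support them.

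- A reader might infer that the participation comparison is biased in the same way. The planned measure is an odds ratio, and the ineligible share cancels from it or nearly so. Moving it to all randomised people would pull it away from its value among eligible people.
- A reader might infer that CRC mortality is affected. Section 5 follows all randomised subjects whether or not they were screened. The intention-to-treat part of the SAP compares the invitation arms from the day of randomisation. Within the SAP, the eligible denominator appears only in item 1 of the secondary end points.
- A reader might say that the plan presents yield as its intention-to-screen measure. The SAP does not label it so; it openly defines yield per eligible individual.

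**Conclusion.** The point holds for diagnostic yield and for the percentages reported per eligible person. Following the plan as written favours the arm with higher attendance, whichever that turns out to be. The yield ratio is inflated by about 0.5-2% at 35/25% attendance and 1-4% at 40/20%, if 5-20% of attenders are excluded. These sizes rest on assumed attendance and exclusion shares, on attendance being independent of ineligibility, and on exclusions being found only among attenders. Better ascertainment in non-attenders would reduce them, and equal attendance would remove them. The bias is unlikely to create or hide a large difference in yield, but it is avoidable. The planned participation odds ratio and the mortality analysis are outside this conclusion.

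**What to change.** In item 1 of the SAP's secondary end points, make the intention-to-screen comparison of diagnostic yield on all randomised people. Remove only those found ineligible from pre-randomisation records searched alike in both arms. In the illustration this takes the distortion to zero for every attendance pair. Keep the per-eligible yield as a secondary presentation. The first-round analysis was scheduled for July 2011 (section 8), so for that round report the all-randomised result alongside the per-eligible one. Report exclusions by arm, by reason and by source (record search, appointment, or contact with non-attenders), so that a reader can see how far the two denominators diverge.

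The cost is SAP wording, one additional analysis and slightly lower yield percentages. The per-eligible participation odds ratio can stay as planned.
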